The study as detailed within this research protocol plan will be conducted in accordance with the principles of Good Clinical Practice, the UK Policy Framework for Health and Social Care Research, the Declaration of Helsinki, and the current regulatory requirements, including the Medicines for Human Use (Clinical Trials) Regulations 2004 (UK S.I. 2004/1031) and all subsequent amendments, and ICH E9 - Statistical principles for Clinical Trials and ICH E10 - Choice of Control Groups.

I take responsibility for ensuring the statistical work in this protocol is accurate, and for the statistical analysis and oversight of this study.

Statistician name: [name]

Signature:

Date:

Principal Investigator Agreement

The clinical study as detailed within this research protocol (**version 2.0, dated 22/04/25**), or any subsequent amendments, involves the use of an investigational medicinal product and will be conducted in accordance with the UK Policy Framework for Health and Social Care Research, the World Medical Association Declaration of Helsinki (1996), Principles of ICH-GCP, and the current regulatory requirements, as detailed in the Medicines for Human Use (Clinical Trials) Regulations 2004 (UK S.I. 2004/1031) and any subsequent amendments of the clinical trial regulations.

Principal Investigator:

NHS site:

Signature:

Date:

4. Summary and synopsis

Short title	ASiCS-II
Study design	Double-blind randomised controlled superiority trial
Objectives	
Primary objective
 
 To assess and draw inference on the efficacy of a 10-day ketogenic enteral feeding regimen compared with standard enteral feeding in increasing the number of sit-to-stand repetitions performed in 30 seconds, 30 days after randomisation in critically ill patients. 
Secondary objectives
 
 To assess and draw inference on the difference between the 10-day ketogenic enteral feeding regimen and standard enteral feeding for the Core Outcome Set measures of functional recovery (mortality, SF-36, Barthel Index) 30 days after randomisation. To provide safety data on the use of a 10-day ketogenic enteral feeding regimen in critically ill patients compared with standard enteral feeding during the intervention period. 
Mechanistic objectives
 
 To collect routinely measured daily serum urea and creatinine data during the 10-day intervention period as biochemical markers of catabolism. To examine alterations in the causal pathway between trial arms (differential ketone and amino acid flux, urea cycle flux and tricarboxylic acid cycle intermediate generation) using serum metabolomics from samples on day 1 and 7 post-randomisation. To confirm the induction of ketosis at seven days post-randomisation.
Number of participants	282 patients
Inclusion and exclusion criteria	
Inclusion criteria
 
Adults (≥ 18 years) admitted to critical care units who are
 
EITHER:
 
 Hospitalised with acute respiratory failure ($\text{PaO}_2/\text{FiO}_2$ ratio of ≤ 39.9 KPa)* 
AND

	
 • Expected to require advanced respiratory support (High-Flow Nasal Oxygen, non-invasive or invasive ventilation for >48 hours)^{\$} AND • C-reactive Protein ≥ 75 mg/l indicating systemic inflammation* AND • Nasogastric feeding planned for >48 hours^{\$} 
OR
 
 • In multi-organ failure (Sequential Organ Failure Assessment Score [SOFA] Score ≥ 2 in two or more domains)* AND • Nasogastric feeding planned for >48 hours^{\$} 
Exclusion criteria
 
 • Pre-existing inability to perform a sit-to-stand test (e.g., significant cognitive impairments that would impact their ability to engage in physical activity testing, Clinical Frailty score of ≥ 6, amputations, acute or chronic disability expected to preclude the sit-to-stand test at 30 days. amongst others)^{\$} • New (pre-randomisation) inability to perform a sit-to-stand test. e.g., Primary neuromyopathy, acute intracerebral pathology, new or existing weight bearing restrictions or new neurological impairment amongst others)^{\$} • Deemed unlikely to survive to 30 days OR presence of a treatment limitation^{\$} • Contraindications to nasogastric feeding[^] • Clinical need for specialist feeds[^] • Patients with known inborn errors of metabolism[^] 
* Most recent recording from the first 24 hours of hospital admission
 
^{\$} as confirmed by the treating clinician
 
[^] absence of these criteria in the medical notes will be considered to indicate no concern

Statistical methodology and analysis	
The primary outcome analysis is a survivor analysis. The treatment effect is the difference in the mean 30-Second Sit-To-Stand among participants who survive to 30 days follow-up under intervention and control. The treatment effect will be estimated using a linear mixed model adjusted for site (random effect), age and functional co-morbidity index. The main analyses of primary and secondary outcomes will be conducted using multiple imputation under a missing at random assumption for those

	participants lost to follow-up. Controlled multiple imputation analysis using a δ -based imputation approach will be performed as sensitivity analyses. We will estimate the survivor average causal effect and assess consistency with the main primary outcome treatment effect estimate.
Study duration	48 months

5. Introduction

Our overarching aim is to prevent muscle wasting which affects the majority of the 16000 patients admitted daily as emergencies to NHS hospitals in England, helping them regain the quality of life and physical independence they enjoyed before hospital admission.¹ Every month 50000 patients stay for >7 days in hospital, losing muscle mass, developing new physical impairment and need for social care support, delaying their discharge.¹⁻⁴ The most seriously ill patients, those in intensive care, lose muscle rapidly. A 70-kilogram patient in intensive care will lose 1-2 kilograms of muscle every day.⁵ Of the 120,000 patients a year that survive critical illness, 98% develop physical functioning impairments, resulting in loss of physical independence.⁶⁻⁸ At 12 months, 70% of survivors have substantial functional limitations and 30% remain carer-dependent.^{8,9} Exercise can only increase or maintain muscle mass in conjunction with effective nutrition.^{10,11} Many high-quality trials have failed to yield an intervention that improves physical independence.^{12,13} The lack of successful interventions is felt by patients. One of our PPI members stated in regard to our planned trial, "*I wish there was something like this in place rather than throwing endless prescription calorie drinks at me*". One third of previously employed critically ill patients do not return to work within five years.¹⁴ The estimated UK annual excess cost of muscle weakness across health and social care is £25 billion per year.¹⁵ While NICE identified this as a growing public health issue, no specific interventions are recommended due to lack of efficacy data.¹⁶ Patients ranked prevention of muscle wasting in the top three priorities for critical care research in the James Lind Alliance research priority setting exercise.

Carbohydrates, fat or protein cannot maintain muscle mass in critically ill patients

Muscle mass is maintained by a balance between synthesis and breakdown.¹⁷ Muscle protein synthesis is a very highly energy dependent process and is low in critically ill patients, and does not respond to increased protein delivery.^{5,18} Muscle protein breakdown is increased in an attempt to use protein for energy.^{5,19} Current medical nutrition therapy is ineffective as carbohydrates, fats and protein cannot be utilised effectively to produce energy because of tissue inflammation and hypoxia, leading to rapid muscle wasting.²⁰⁻²²

Ketogenic feeds may help patients regain independence by maintaining muscle mass

Ketogenic feeding involves stimulating hepatic synthesis of ketone bodies. Hepatic metabolism of medium-chain triglycerides (MCTs) can yield ketone bodies such as beta-hydroxybutyrate and acetoacetate and is not affected by hypoxia or inflammation.²³

Ketogenic feeding represents a frame shift in critical care nutritional research. Ketone derived energy would increase muscle protein synthesis and decrease muscle protein breakdown. Ketones are used for energy in high-intensity exercise and starvation, sparing muscle.²⁴⁻²⁷ Ketogenic diets have been used to treat epilepsy and are being investigated for use in traumatic brain injury, neurodegenerative diseases, non-alcoholic fatty liver disease, diabetes and heart failure.²⁸⁻³³

A proof-of-concept trial demonstrated safety, feasibility and a signal for efficacy

We performed a randomised controlled trial to determine the feasibility and safety of delivering a ketogenic enteral feed in critically ill patients as step-change intervention to prevent muscle wasting and loss of physical independence.³⁴ This was necessary for a number of reasons. Ketoacidosis might occur if ketones were not metabolised, exacerbating pre-existing systemic and cellular acidosis that carries a mortality risk to critically ill patients. Ketogenic diets minimise exogenous glucose delivery, which might predispose patients to hypoglycaemia, which is harmful to patients³⁵. Lastly, a ketogenic high lipid feed might increase the risk of vomiting (and therefore pulmonary aspiration), diarrhoea and pancreatitis.³⁶

Ketosis was achieved within 48 hours and sustained for the 10-day intervention period. Ketogenic feeding was demonstrated to be safe. Ketogenic feeding resulted in less hypoglycemia (0.0% vs. 1.6% events) and hyperglycemia (26.9% vs. 57.5% events), lower glucose co-efficient of variation (9.4% vs. 14.8%), and lower cumulative insulin use (0IU (IQR 0-16) vs. 78 IU (IQR 0-412)). The trial process was considered acceptable and feasible. A mean score of 8/10 (with 10 scored as the most positive response) was obtained for the question '*How keen would you be to work on another similar study?*'. A signal that ketogenic feeding may reduce muscle wasting was seen in the metabolomic data (decreased muscle protein breakdown) and clinical markers of catabolism such as urea were lower in the ketogenic arm by day eight and persisted until the end of the study period (8.7 (95%CI 6.4-19) vs. 12 (95%CI 10-19), as was the Urea-to-Creatinine ratio (117 (95%CI 93-206) vs. 168 (95%CI 102-235)). Lastly the median Chelsea Critical Care Physical Assessment score at hospital discharge was higher in the ketogenic feeding arm ((34 (95%CI 22-45) vs. 25 (95%CI 8-46)).

6. Risks and benefits

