6.1 Summary of potential risks

Participants allocated to receiving the ketogenic feed could be susceptible to ketoacidosis if the ketones are not metabolised. This could exacerbate pre-existing systemic and cellular acidosis that carries a mortality risk to critically ill patients. There is a possibility that ketogenic diets can also minimise exogenous glucose delivery, predisposing patients to hypoglycaemia, which is harmful.³⁵ Lastly, ketogenic enteral feeds with a high lipid content could increase the risk of vomiting (and therefore pulmonary aspiration), and diarrhoea. However data from previously studies including our recently published trial (ASiCS) does not support concerns of acidosis, hypoglycaemia or vomiting, indicating that the feed is safe.^{34,37-45} It may be that ketogenic feeding reduces glucose variability and hypoglycaemia, decreasing harm to patients, an observation also seen in other ketogenic feeding trials in the critically ill.^{34,46,47} The signal for increased diarrhoea is unclear, as diarrhoea is extremely common in critically ill patients.³⁶

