7.6 Safety outcome measures

- New (post initiation of intervention) metabolic acidosis (Base Excess of >4 mEq/l) not in keeping with the clinical condition, in the opinion of the treating clinician within 10 days of randomisation.
- Hypoglycaemia episodes not in keeping with the clinical condition (normoglycaemia defined as 4.0-10.0 mmol/l), assessed from routine blood monitoring within 10 days from randomisation.

- Hyperglycaemia episodes not in keeping with the clinical condition (normoglycaemia defined as 4.0-10.0 mmol/l) assessed from routine blood monitoring within 10 days from randomisation.
- Days when an episode of diarrhoea (defined as a Bristol School Score ≥ 5) is recorded on nursing observation charts during the first 10 days from randomisation.
- Days where an episode of vomiting is recorded on nursing observation charts during the first 10 days from randomisation.
- Nausea defined as when an anti-emetic is given for patient-reported nausea assessed daily during the first 10 days from randomisation.

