11.1 Study intervention risks

Published data on our ASiCS trial that specifically set out to assess safety does not support worries of acidosis, hypoglycaemia, or vomiting.³⁴ The signal for increased diarrhoea is unclear, as diarrhoea is extremely common in critically ill patients. For ASiCS-II, pre-defined safety data will be collected on acid-base balance, glucose control, and gastrointestinal intolerance (specifically on vomiting and diarrhoea). All such side effects would occur during the acute inpatient stay and therefore detected directly by the study team. Furthermore the Data Monitoring and Ethics Committee (DMEC) will monitor safety data throughout the trial and will routinely meet to assess safety analyses.

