15.1 Data Management

Pseudonymised trial data will be transcribed onto the electronic CRF (eCRF) on the secure data entry web portal. All data will be pseudonymised at site, and a trial ID generated by the database. Age, patient initials and the trial ID will be used to identify the participants. The CRF will be designed by the database manager in the Critical Care and Perioperative Medicine Research group with input from the CI in accordance to Sponsor requirements. Only trial data related to the outcomes and data including safety events that will be used for statistical analysis will be collected. For participants that are withdrawn, data collected up to the point of withdrawal will be retained. Handling of withdrawal in terms of statistical analysis will be fully detailed in the statistical analysis plan.

Submitted data will be reviewed for completeness and consistency by authorised users within the trial coordinating team. Direct access to eCRF will be restricted, with only delegated and authorised users will be issued with (trial role related and defined) access to the eCRF. Each user will be assigned specific user roles and rights, and this will be reflected on the respective delegation log. Final sign-off by the site PI will be undertaken. Following data cleaning, a single final data lock will prevent changes to protect the final data set and will be exported from the study database for analysis by the trial statistician.

Storage and handling of confidential trial data and documents will be in accordance with the Data Protection Act 2018 (UK). A trial specific Data Management Plan will be developed by the coordinating team detailing all key methods of data management for collecting, recording, handling and storing of trial data. Transfer of patient identifiable information [contact] accounts and those used in [contact] will be secure and meet appropriate IT encryption and data protection requirements.

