18.3 Notification and reporting of AEs and ARs

The AE will be documented in the participants' medical records and the electronic Case Report Form (eCRF). The participant will be followed up by the research team until the AE is resolved.

The following safety events will be required for daily reporting from the point randomisation until day 10 and recorded in the eCRF. These events won't be reported as AEs:

- Acid-Base balance disruption, defined as unexpected acidosis not in keeping with the clinical condition, in the opinion of the treating clinician. The absence of documentation in the medical notes will be considered to indicate no concern.
- Hypoglycaemia episodes (normoglycaemia defined as 4.0-10.0 mmol/l), assessed from routine blood monitoring. Where no routine blood monitoring occurs, normoglycaemia is assumed.
- Hyperglycaemia episodes (normoglycaemia defined as 4.0-10.0 mmol/l) assessed from routine blood monitoring. Where no routine blood monitoring occurs, normoglycaemia is assumed.
- Diarrhoea defined as a Bristol School Score ≥ 5 .
- Vomiting defined as $>10\text{ml}$ of vomitus.
- Nausea defined as when an anti-emetic is given for patient-reported nausea.

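### Pancreatitis is named in section 5 as a possible harm of the high-lipid feed, but it is dropped from the risk summary and has no solicited record or planned by-arm report

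*Protocol*

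**What the plan says.** The proof-of-concept part of section 5 explains why a pilot was needed. Besides ketoacidosis and hypoglycaemia, it says that "a ketogenic high lipid feed might increase the risk of vomiting (and therefore pulmonary aspiration), diarrhoea and pancreatitis".

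Section 6.1, the risk summary for the present trial, says that "ketogenic enteral feeds with a high lipid content could increase the risk of vomiting (and therefore pulmonary aspiration), and diarrhoea". It then states that earlier data, including the pilot, "does not support concerns of acidosis, hypoglycaemia or vomiting, indicating that the feed is safe".

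Section 7.6 lists six safety outcomes: metabolic acidosis, hypoglycaemia, hyperglycaemia, diarrhoea, vomiting and nausea. Vomiting, for example, is counted as "Days where an episode of vomiting is recorded on nursing observation charts during the first 10 days from randomisation". Section 11.1 says that "pre-defined safety data will be collected on acid-base balance, glucose control, and gastrointestinal intolerance (specifically on vomiting and diarrhoea". Section 18.3 states that "The following safety events will be required for daily reporting from the point randomisation until day 10 and recorded in the eCRF", followed by the same six topics as 7.6.

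Two other routes exist. For adverse events in general, 18.3 says that "The AE will be documented in the participants' medical records and the electronic Case Report Form (eCRF". For serious events, 18.4 restricts site reporting to those that are both related and unexpected, where unexpected means not listed in the protocol as an expected occurrence.

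**The concern.** The protocol raises a specific, potentially serious harm, ties it to the fat content of the feed, and then does not mention it again. No reason is given for dropping it between section 5 and section 6.1. The other harms that section 5 names, apart from pulmonary aspiration, each have a defined outcome and a daily record.

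At stake is what the trial can say at its end. A secondary objective in 7.2 is to provide safety data on the ketogenic regimen against standard feeding. Under 20.3 the DMEC looks for patterns that single cases would not show. For a harm that nobody is prompted to record, an absence of reports cannot be told apart from an absence of looking.

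**Working it through.** **Step 1. Compare the places where the feed's harms are listed.**

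| Place in the protocol | Harms named or tracked | Pancreatitis? |
|---|---|---|
| Section 5, reasons for the pilot | ketoacidosis, hypoglycaemia, vomiting (with aspiration), diarrhoea, pancreatitis | Yes |
| Section 5, pilot results | ketosis, glucose control, insulin use, urea markers, physical function, general statement of safety | No |
| 6.1 | ketoacidosis, hypoglycaemia, vomiting (with aspiration), diarrhoea | No |
| 7.6 | six outcomes | No (0 of 6) |
| 11.1 | acid-base, glucose, vomiting, diarrhoea | No |
| 18.3 daily list | the same six topics | No (0 of 6) |
| Appendix 1 | events exempt from regulatory reporting | No |

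The word occurs once in the protocol. The reassurance in 6.1 and 11.1 covers acidosis, hypoglycaemia and vomiting only, so the concern is neither answered nor withdrawn.

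**Step 2. Trace how a case could be recorded.**

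- *General AE.* Section 18.3 requires AEs to be entered in the eCRF and sets no relatedness condition. Only the six listed events are taken out of AE reporting, so a diagnosed pancreatitis would qualify. The schedule in 9.13 marks AE/SAE review for days 2 to 10 only, and nothing asks about pancreatitis.
- *SAE.* The event must be judged related and unexpected. The protocol does not say whether a possible harm mentioned in section 5 counts as expected, so sites could decide differently.
- *Record review.* Sections 9.9 and 9.13 already provide for review of medical records to day 30, but no item in it concerns pancreatitis.

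**Step 3. Size, conditional on an assumed rate.** The protocol states no pancreatitis rate, so the rates below are assumptions shown as a range. Patients on the ketogenic feed: 282 / 2 = 141, from 12.2 and the 1:1 allocation in 9.4, taking all as fed as allocated and fully observed.

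Chance of at least one case = 1 − (1 − p)^141:

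| Assumed true rate p | Chance of at least one case |
|---|---|
| 0.1% | 1 − 0.999^141 = 13% |
| 0.5% | 1 − 0.995^141 = 51% |
| 1% | 1 − 0.99^141 = 76% |
| 2% | 1 − 0.98^141 = 94% |

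**Step 4. What zero cases would show.** The one-sided upper 95% limit by the rule of three is 3 / 141 = 2.1%. The exact form, 1 − 0.05^(1/141), also gives 2.1%.

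**Step 5. What a comparison would show.** Power by the normal approximation, two-sided 5%, 141 per arm:

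- 1% against 2%: standard error = √[(0.0099 + 0.0196)/141] = 0.0145; 0.01/0.0145 = 0.69; power = Φ(0.69 − 1.96), about 10%.
- 1% against 5%: standard error = √[(0.0099 + 0.0475)/141] = 0.0202; 0.04/0.0202 = 1.98; power = Φ(1.98 − 1.96), about 50%.

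The approximation is rough for such small counts, but it shows that a by-arm table would be descriptive only.

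**The case against.** The sentence in section 5 is background. It gives the reasons for an earlier trial, says only that the feed might raise the risk, and is followed by the claim that the pilot showed the feed to be safe. Section 6.1 is the current risk statement, and authors may drop a theoretical concern after a pilot. This is a fair reading of intent, but the protocol does not say so and reports no pilot finding on pancreatitis.

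A reader might infer that the trial cannot record or compare pancreatitis at all. The protocol does not support that. General AE entry is open to it, the DMEC reviews overall safety data, and a by-arm AE table could stand in the SAP, which is not shown. Nor does the wording in 15.1, "Only trial data related to the outcomes and data including safety events that will be used for statistical analysis will be collected", bar AE entry, since 18.3 expressly requires it. Appendix 1 exempts events from regulatory reporting rather than from the eCRF; its entry for abdominal pain concerns a symptom, not this diagnosis.

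A reader might also infer that pancreatitis is the only named harm left out. It is not: pulmonary aspiration has no item of its own either, although vomiting, its stated pathway, is tracked. Nor can it be said that cases are likely, because that depends wholly on an assumed rate.

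What remains is that the general AE route has no definition, no prompt and a short scheduled window, and an SAP cannot add a field that sites were never asked to complete.

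**Conclusion.** The point holds in a limited form. The risk statements in sections 5 and 6.1 differ without explanation, and a harm that the protocol links to the feed has no solicited ascertainment and no planned by-arm report. Capture is possible but left to chance. The gap does not touch the primary analysis, and it does not leave the safety objective as a whole unanswered.

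With systematic collection, zero cases in 141 patients would support an upper limit near 2.1%. Under unsolicited recording, a limit could be stated only for cases that happened to be diagnosed and entered. This rests on full ascertainment in 141 patients; the safety population in 8.5, defined by feed received, may differ somewhat. It is a worthwhile, inexpensive improvement rather than a flaw that threatens the trial.

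**What to change.** 1. Reconcile sections 5, 6.1, 7.6, 11.1 and 18.3. Either carry pancreatitis through them or state why it is no longer considered a risk, with the supporting data.
2. Add one yes/no eCRF field: new clinical diagnosis of pancreatitis recorded in the medical notes. Collect it regardless of relatedness, from the record review already scheduled to day 30. State the reporting window, because 7.2 frames safety over the 10-day intervention period.
3. Report it descriptively by arm, without a test, and include it in DMEC reports.
4. State whether pancreatitis is an expected occurrence for SAE reporting under 18.4.

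The cost is one field, one table row and a wording amendment. No blood test, visit, dose or treatment rule changes. The drawback is that relying on diagnoses in the notes may miss mild cases, though blinding should make this similar in the two arms.
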